2.2.2. Clinic associated with COVID-19 infection

In the longest series published by the China Center for Disease Control, describing the characteristics of all cases detected in mainland China from the beginning of the outbreak to February 11, 2020 (72,314 cases), 1.2% of cases were asymptomatic⁽⁸⁾. These cases were detected in the context of exhaustive searches in intrafamilial outbreaks⁽⁹⁾ and some ended up developing symptoms⁽¹⁰⁾. In contrast, on the Diamond Princess ship, quarantined in Japan, where diagnostic tests were carried out on 3,700 passengers, 50% of those who had positive results were asymptomatic.^(11,12). Subsequently, after 14 days of observation, the majority developed symptoms, with the percentage of truly asymptomatic being 18% (95% CI: 15.5-20.2). Asymptomatic cases are more frequent in children and it has been observed that some of them present pulmonary radiological alterations, such as multifocal opacities and analytical alterations, such as elevated phosphatase.

The report of the WHO mission to China describes the most common symptoms and signs of 55,924 laboratory-confirmed cases, including: fever (87.9%), dry cough (67.7%), asthenia (38.1%), expectoration (33.4%), dyspnea (18.6%), sore throat (13.9%), headache (13.6%), myalgia or

arthralgia (14.8%), chills (11.4%), nausea or vomiting (5%), nasal congestion (4.8%), diarrhea (3.7%), hemoptysis (0.9%), and conjunctival congestion (0.8%)⁽¹³⁾. In Europe, with 14,011 confirmed cases reported to the European Surveillance System (TESSy) by 13 countries (97% of Germany), the most frequent symptoms were: fever (47%), dry or productive cough (25%), sore throat (16%), asthenia (6%) and pain (5%). In Spain, with 18,609 reported cases, the most frequent

Características clínicas	Yang (n=52) *	Chen (n=99)	Wang (n=138)	Guan (n=1099)
	%	%	%	%
Signos y síntomas				
Fiebre al ingreso	98,0	83,0	98,6	43,1
Tos	77,0	82,0	59,4	67,8
Astenia/Malestar	35,0	ND	69,6	38,1
Anorexia	ND	ND	39,9	ND
Mialgias	11,5	11,0	34,8	14,9
Disnea	63,5	31,0	31,2	18,7
Expectoración	ND	ND	26,8	33,7
Dolor de garganta	ND	5,0	17,4	13,9
Diarrea	ND	2,0	10,1	3,8
Náuseas/vómito	4,0	2,0	10,1	5,0
Mareo	ND	ND	9,4	ND
Cefalea	6,0	8,0	6,5	13,6
Escalofríos	ND	ND	ND	11,5
Hallazgos Radiológicos				
Infiltrados alveolares unilaterales	ND	25,0		ND
Infiltrados alveolares bilaterales	ND	75,0	100	51,8
Infiltrados intersticiales	ND	ND		14,7
Patrón de vidrio esmerilado	ND	14,0		56,4

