3. OBJECTIVES

3.1. Main objectives

- Describe the population infected by COVID-19 with genitourinary tumors (urothelial cancer, prostate cancer, testicular cancer and renal cancer) treated in Spanish hospitals, know the clinical presentation, therapeutic evolution and prognosis of said intercurrent infectious process, as well as its possible relationship with different clinical and therapeutic factors.
- Assess the possible relationship of the different oncological treatments administered to these patients with the clinical evolution of COVID-19 infection, considering both patients who have undergone oncological treatment previously, during or after COVID-19 infection.
- To specifically evaluate the impact of COVID-19 infection on the toxicity of immunotherapy treatment (mainly pneumonitis) and the impact of immunotherapy on the evolution of the infectious condition in patients with tumors of genitourinary origin, in three different scenarios: during treatment, after treatment and in patients who are prescribed treatment after the infection has passed.
- Analysis of this same relationship in patients with genitourinary tumors and asymptomatic COVID-19 infection with positive Ab serologies (IgM and IgG).
- To evaluate in patients with Prostate Cancer (PCa) the impact of androgen deprivation therapy (ADT) and new antiandrogen agents (NAH) with or without corticosteroids on infection COVID-19.

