4. STUDY METHODOLOGY

4.1. Study type and design

This is a national multicenter, observational, retrospective and prospective post-licensure (EPA-AS) study that will include patients with genitourinary tumors presenting with COVID-19 infection.

The study will be carried out in Spanish hospital centers, with principal investigators belonging to the medical oncology services of the SOGUG group (Spanish Genitourinary Oncology Group), who will act as sponsor. Once the patients are selected, the variables described in section 5 of this protocol will be collected and studied.

The study will use data obtained from the patient's medical history, with no plans to use other sources.

The assignment of a patient to a specific therapeutic strategy has already been decided in advance by the usual clinical practice of medicine; The decision to prescribe a specific treatment is clearly dissociated from the decision to include a patient in the study. No intervention, whether diagnostic or follow-up, will be applied to patients other than standard clinical practice. Epidemiological methods will be used to analyze the data collected.

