4.3. Inclusion criteria

- Patients ≥18 years old.
- Diagnosed with genitourinary cancer (urothelial, kidney, prostate and germ cell).
- COVID-19 infection prior to oncological treatment, during treatment or after treatment.
- COVID-19 infection must be confirmed by PCR or serology, regardless of whether or not the patient requires hospitalization due to the infection. Additionally, clinical and/or radiological determination must be available in those patients who present symptoms.

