5. VARIABLES

5.1. Study variables

A data collection notebook will be prepared in which the following variables will be collected for analysis:

Affiliation of the center:

- Hospital name
- Province
- Investigator's name
- Patient number

Patient characteristics:

- Age
- Sex
- Age
- Hospital center where the patient is recruited (in order to have epidemiological data on the pandemic that may be of interest)

Pathological history:

- Concomitant pathology (cardiac, pulmonary, renal, liver, Diabetes Mellitus, HIV, AI)
- Usual pharmacological treatment
- Smoking and alcohol habit

Tumor pathology:

- Tumor type, histology and stage (initial and at diagnosis of infection)
- Date of cancer diagnosis
- Active cancer treatment or follow-up
- Participation in clinical trial
- Type of treatment most recently received for the infection (Surgery; Radiotherapy; Chemotherapy: Drug, Immunotherapy, TD: Drug, HT: ADT alone or with Abiraterone, Enzalutamide, others)
- Treatment lines
- Start and last dose received of the most recent oncological treatment

For patients with prostate cancer:

- Local treatment and type (Surgery, Radiotherapy)
- Adjuvant ADT or advanced disease (start date)
- NAH (date and line of treatment)
- Associated corticosteroid treatment: Prednisone vs Dexamethasone (dose)

COVID-19 infection data:

- Confirmation date of COVID-19 infection
- PCR diagnostic test
- IgG or IgM serological diagnostic test
- Present symptoms

- Analytical alterations, lymphopenia, elevated CRP, high D-dimer.
- Thrombosis associated with COVID-19 infection
- Date of onset and disappearance of symptoms
- Days duration of fever and cough
- Radiological examination at the moment of greatest severity
- Complications of infection: presence of complications and/or hospital or ICU admission
- Admission date
- Date of most serious complication
- Treatments received for COVID-19
- Discharge status
- Fecha de alta / exit
- Negativization of the presence of viruses by PCR
- Negative PCR date

For patients who are receiving or have received immunotherapy treatments, additional information will be collected:

- Immunotherapy treatment line
- Start/end date of immunotherapy treatment
- Date of last dose received prior to COVID-19 infection
- Immunotherapy received as monotherapy or combination
- Type of immunotherapy
- Adverse effects

Prospective follow-up data (6 months from patient inclusion):

- Date of start or restart of oncological treatment after infection

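### One positive serology can be the only evidence of infection in an asymptomatic patient, and sections 3.1, 4.3 and 5.1 do not settle whether IgM, IgG or both are required, so the asymptomatic percentage, and possibly objective iv, may count never-infected patients

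*Combined protocol and SAP*

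**What the plan says.** The entry rule in section 4.3 reads "COVID-19 infection must be confirmed by PCR or serology", and it applies whether or not the patient was admitted. It adds that "clinical and/or radiological determination must be available in those patients who present symptoms". Nothing comparable is asked of patients without symptoms, and no assay, antibody class, threshold or repeat result is specified. Section 4.4 has no exclusion criteria. Section 4.1 rules out testing for study purposes: "No intervention, whether diagnostic or follow-up, will be applied to patients other than standard clinical practice".

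The fourth main objective in section 3.1 (item iv in the summary, section 1.2) concerns "asymptomatic COVID-19 infection with positive Ab serologies (IgM and IgG"). Section 5.1 lists PCR as one variable and "IgG or IgM serological diagnostic test" as another.

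The third secondary objective in section 3.2 is the share of enrolled patients who had no symptoms or only mild ones. The analysis text in section 4.5 names chi-square, t-test or ANOVA, and Kaplan-Meier with log-rank. It plans no analysis by how infection was confirmed.

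**The concern.** In a symptomatic patient the test result is backed by a clinical or radiological picture. In an asymptomatic patient the test may stand alone. How often a lone positive result is wrong depends on the assay's specificity and on how likely infection was before testing, and the plan controls neither.

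A never-infected patient counted as an asymptomatic case adds one to both numerator and denominator of the asymptomatic percentage and so raises it. If one antibody is enough for objective iv, such patients also enter the group in which the relation between immunotherapy and toxicity or course of infection is studied. That relation cannot exist in people who never had the infection. Whether they enter depends on how IgM and IgG is read, and the three sections leave this open.

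**Working it through.** **Inputs from the documents.** The entry rule (4.3), the absence of exclusions (4.4), the absence of added testing (4.1), the two antibody wordings (3.1, 5.1) and an expected total of about 250 (4.5). There is no stated false-positive figure to reproduce, and the 250 has no error rate, power or effect size behind it. Section 2.2.2 reports that in a large Chinese series "1.2% of cases were asymptomatic", and 18% on the quarantined ship. Those are shares of infected people without symptoms, not the probability that a tested asymptomatic person is infected, so they cannot serve as the prior.

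**Assumed inputs.** Sensitivity Se = 0.90, specificity Sp from 0.95 to 0.998, prior probability p from 2% to 20%.

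**Step 1, one positive result.** False-positive share = (1 - p)(1 - Sp) / [p x Se + (1 - p)(1 - Sp)].

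Example, p = 0.05 and Sp = 0.98: 0.95 x 0.02 = 0.019; 0.05 x 0.90 = 0.045; 0.019 / 0.064 = 29.7%.

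| Sp | p = 2% | 5% | 10% | 20% |
|---|---|---|---|---|
| 0.95 | 73% | 51% | 33% | 18% |
| 0.98 | 52% | 30% | 17% | 8% |
| 0.99 | 35% | 17% | 9% | 4% |
| 0.998 | 10% | 4% | 2% | 1% |

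Lowering sensitivity to 0.80 moves the upper end only from 73% to 75%.

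**Step 2, the two readings of the antibody wording.** Take Se = 0.90 and Sp = 0.98 for each antibody, with independent errors.

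- Either positive: Se = 1 - 0.10² = 0.99, Sp = 0.98² = 0.9604. False-positive shares are 66%, 43%, 26% and 14% at p = 2%, 5%, 10% and 20%.
- Both positive: Se = 0.90² = 0.81, 1 - Sp = 0.02² = 0.0004. Shares are 2.4%, 0.9%, 0.4% and 0.2%.

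At p = 5% the choice of reading moves the share from 43% to 0.9%. Correlated errors between the two antibodies would narrow that gap.

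**Step 3, effect on the asymptomatic percentage.** Suppose 40 of 250 patients are asymptomatic on a single serology and no others are asymptomatic. The 40 is an assumption; the documents give no count. The reported share is 40/250 = 16%.

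- At 30% false positives, 12 were never infected: 28/238 = 11.8%.
- At 73%, about 29: 11/221 = 5%.
- At 1%, fewer than one, and the figure stays at about 16%.

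**Step 4, effect on an association.** Assume true event rates of 0.30 and 0.10 in two treatment groups.

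- False positives 30% in both groups, with event rate 0.10 in each: 0.7 x 0.30 + 0.3 x 0.10 = 0.24, so the difference falls from 0.20 to 0.14. The number per group for 80% power (two-sided 5%) rises from 62 to 112. Power at 62 per group falls from 80% to 55%.
- False positives 30% in both groups, with no events: 0.21 against 0.07. The difference is 0.14, but the ratio is still 3.0.
- False positives 10% of the exposed and 30% of the unexposed, with no events: the observed ratio is the true ratio x 0.9/0.7. A true 1.0 appears as 1.29 and a true 3.0 as 3.86, away from the null. With the shares reversed the factor is 0.7/0.9, giving 0.78 and 2.33.

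**The case against.** The strongest reply is that 4.3 governs entry to the study, not membership of the objective iv group. Objective iv describes its own group and names both antibodies. If both must be positive, a patient with one antibody is in the study but not in that group, and step 2 gives a false-positive share of about 1% at a 5% prior. This stands as a possible reading. It is not the only one, because the parenthesis may merely list the two antibody classes, and neither 4.3 nor 5.1 enforces it. It also leaves the asymptomatic percentage untouched, since that covers everyone admitted under 4.3.

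Second, the size rests wholly on assumed accuracy and prior. This stands too. The documents do not say why asymptomatic patients were tested, and the examples in section 2.2.2 (family outbreaks, a quarantined ship) are high-exposure settings. If testing followed contact with a case, the low priors in the table are too pessimistic.

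Third, a reader might infer that 5.1 shows one merged data field. It does not. It lists topics for a form still to be prepared, and the form is not in the documents. PCR is listed separately, so patients confirmed by serology alone should be identifiable.

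**Conclusion.** The point holds in a limited form. The entry rule allows a single serology to be the only evidence of infection in an asymptomatic patient, and the three sections do not settle which antibody rule defines objective iv. The false-positive share among such patients lies anywhere from about 1% to 73% under the assumed ranges, and the plan includes no analysis that would show how far the results depend on these patients. Any false positives raise the asymptomatic percentage; how far depends on a count that the documents do not give.

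Three stronger readings are not supported:

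- That the objective iv group does contain a large share of false positives. It may not, if both antibodies are required or specificity is high.
- That any real effect is diluted. Dilution is the usual direction when false positives are unrelated to treatment, but a ratio can be unchanged, and differential false positives can push it either way.
- That reported mortality must fall. The secondary objective is status at discharge, and patients never admitted may not be in that denominator.

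**What to change.** 1. Reconcile 3.1, 4.3 and 5.1: state whether objective iv means IgM, IgG or both.
2. Record IgG and IgM as separate results, each with its date.
3. Report objective iv and the asymptomatic percentage by mode of confirmation: PCR positive; IgM and IgG both positive; single isolated serology. State in advance where a repeated positive of one antibody class belongs, since errors on repeat tests in the same patient may be correlated.
4. Add a sensitivity analysis of both that leaves out patients whose only evidence is one isolated serology result.

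This uses chart data only. It needs no new test, and every patient stays in the study. The cost is a clarified definition, separate antibody fields and a short addition to section 4.5. The strata may be small. Patients with more than one result are also those who were tested more often, so differences between strata partly reflect who was tested and should be read that way. For that reason the strata are offered as a description with a sensitivity analysis, not as a requirement for two concordant results in the main analysis.

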4.4. Exclusion criteria

- Not applicable.

As this study is an EPA-AS, all the researchers' activities are carried out in accordance with the center's usual clinical practice. No withdrawal criteria have been established. Information from the clinical history will be collected as long as it does not exist on the part of the researcher, patient refusal to do so. Therefore, those patients who do not attend the corresponding visits will be declared as lost to follow-up, those patients who withdraw their consent to participate, the data collected up to that point will be used for statistical analysis, being lost to follow-up from which the patient withdraws his consent.

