1.2. Methodological aspects

medical product of interest Not applicable
First ethics committee to evaluate the study: Autonomous CEIm of Galicia
Principal Investigators / Coordinators [REDACTED] [REDACTED]

[REDACTED]
 
[REDACTED]
 
[REDACTED]

Researcher/Coordinator Centers:
 
¹ Valencian Institute of Oncology
 
² San Carlos Clinical Hospital of Madrid
 
³ Puerta del Hierro-Majadahonda University Hospital
 
⁴ Lucus Augusti University Hospital, Lugo

Autonomous Communities of Researchers / Coordinators:
 
Valencian Community
 
Autonomous Community of Madrid
 
Galicia

Territorial scope:
 
National, Spain

Information source:
 
Medical records of the patients included after signing informed consent.
 
RETROSPECTIVE PART ONLY: medical records of patients included after signing informed consent or waiver thereof in the cases contemplated (see 6.3 Informed consent).

Type of study (according to the AEMPS classification):
 
EPA-AS

Tracking Type::
 
Ambispective (Prospective and retrospective). A 6-month follow-up is proposed for patients in the prospective part.

Total number of patients expected to include:
 
They are expected to include 250, sufficient to respond to the objectives set by the study.

Planned duration of the study:
 
Data collection 8 months. The estimated duration of the project is 12 to 18 months, depending on the patient inclusion rate.

Study duration for each participant:
 
No specific study visits will be carried out, other than obtaining informed consent in cases where it is required.

Main objectives:
 
a) Main objectives
 
i) Describe the population infected by COVID-19 with genitourinary tumors (urothelial cancer, prostate cancer, testicular cancer and renal cancer) treated in Spanish hospitals, know the clinical presentation, therapeutic evolution and

- prognosis of said intercurrent infectious process, as well as its possible relationship with different clinical and therapeutic factors.
- ii) Assess the possible relationship of the different oncological treatments administered to these patients with the clinical evolution of COVID-19 infection, considering both patients who have undergone oncological treatment previously, during or after COVID-19 infection.

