3.2. Secondary objectives

- To evaluate the mortality associated with COVID-19 infection in the population with genitourinary tumors. Percentage of patients alive/dead at discharge.
- To evaluate the rate (percentage) of complications that have required hospital admission and/or ICU treatment.
- Describe the frequency of asymptomatic or minimally symptomatic COVID-19 infections. Percentage of asymptomatic patients or with mild symptoms included in the study.
- Evolution of the oncological disease. Impact/influence of COVID-19 infection on the effectiveness of oncological treatment. Data will be collected on delays/modifications in follow-up or oncological treatment regimens. The average delay time and the number of modifications will be evaluated. Likewise, it is expected to obtain data on time to progression and overall survival of cancer patients, which can be compared with the reference values for each type of tumor pathology.

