4.9. Study schedule

Study start date (Activation of the first center)	3Q 2020
End date of the study (“Last patient last visit” or end of data extraction)	1T 2021
Study report completion date	2T 2021
Date of first publication	2Q 2021 (expected)

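### Loss to follow-up is defined by non-attendance at unspecified visits in a records-based study, so the 6-month follow-up could be informatively censored

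*Combined protocol and SAP*

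**What the plan says.** The rule stands in section 4.4 of the protocol (Exclusion criteria). That section places it within routine care ("all the researchers' activities are carried out in accordance with the center's usual clinical practice") and states that "No withdrawal criteria have been established". It then says, in an awkward translation, that chart information is gathered unless there is a refusal, and concludes that "those patients who do not attend the corresponding visits will be declared as lost to follow-up". No section defines those visits, their number or a time window, or says whether the chart is still consulted after one is missed. The clause that follows deals with withdrawal of consent: data up to withdrawal are analysed, and the patient counts as lost from then on.

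Other sections bear on the rule:

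- Section 1.2: "No specific study visits will be carried out, other than obtaining informed consent in cases where it is required". Also: "A 6-month follow-up is proposed for patients in the prospective part".
- Section 4.1: "The study will use data obtained from the patient's medical history, with no plans to use other sources".
- Section 3.2, last secondary objective: "Data will be collected on delays/modifications in follow-up or oncological treatment regimens". The summaries are mean delay and number of modifications. Time to progression and overall survival are expected as well.
- Section 4.5: Kaplan-Meier curves and the log-rank test, with no censoring rule and no handling of loss to follow-up.
- Section 5.1: over the 6 months, the date of restart, change or suspension of treatment, date of progression, current status and date of last contact.

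**The concern.** In a study that reads charts, failing to attend an appointment is a poor test of loss. The patient may have been admitted, may be too ill to travel or may have died, and the chart may show it. The missed appointment may also be an instance of the delayed follow-up that section 3.2 sets out to measure.

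Section 4.4 uses the same term, lost to follow-up, for non-attendance and for withdrawal of consent, and for withdrawal it says that data stop. A site could reasonably treat both alike and stop entering data. Two things would then follow. Kaplan-Meier and log-rank assume that censored patients carry the same risk as those still observed, and that may fail here. A patient whose restart date falls after the missed visit would also have no complete delay to contribute, so the mean delay would lean towards patients with short interruptions.

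The protocol shows awareness of this kind of bias in section 6.3. It allows a consent waiver for deceased retrospective patients so that those with the worst outcome are not lost from the sample. The attendance rule could let a similar loss into the prospective part.

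**Working it through.** There is no plan figure to reproduce. The 250 patients in section 4.5 are an expected count, with no loss rate, event rate or power behind them. The check is a reading of the text and then an illustration on assumed inputs.

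**Reading.**

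1. Section 1.2 rules out study-specific visits, not routine ones. Section 4.4 refers to usual practice, and section 4.9 ties study end to "Last patient last visit" or the end of data extraction. The visits are therefore presumably routine appointments, but they are undefined.
2. Section 4.1 makes the chart the only source, and the chart does not close when an appointment is missed.
3. Only outcomes observed during the 6-month prospective follow-up are exposed: delay, time to progression and overall survival. Status at discharge, admission or ICU care and the frequency of asymptomatic infection are not.

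**Illustration (all rates assumed).** Let *h* be the monthly death hazard while attending, *m* the monthly rate of missing a visit, *k* the ratio of the death hazard after a missed visit to that before it, and *T* = 6 months.

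- Kaplan-Meier censored at the missed visit estimates 1 − exp(−*hT*).
- True mortality is 1 − *S*, with *S* = exp(−(*h*+*m*)*T*) + ∫₀ᵀ *m* exp(−(*h*+*m*)*u*) exp(−*kh*(*T*−*u*)) d*u*.
- Inputs: attender mortality of 10%, 20% or 30%, so *h* = −ln(1 − mortality)/6; 5-20% missing a visit by 6 months in the absence of death, so *m* = −ln(1 − proportion)/6; *k* from 1 to 5.

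Worked case with 10% attender mortality, 20% missing and *k* = 3:

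- *hT* = 0.1054, *mT* = 0.2231, and exp(−0.3285) = 0.720.
- The integral is 0.2231 × exp(−0.3161) × (1 − exp(−0.0124))/0.0124 = 0.2231 × 0.729 × 0.994 = 0.162.
- *S* = 0.882, so true mortality is 11.8% against an estimate of 10%.

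True 6-month mortality as the proportion missing rises from 5% to 20%:

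| Kaplan-Meier estimate | *k* = 1 | *k* = 2 | *k* = 3 | *k* = 5 |
|---|---|---|---|---|
| 10% | 10.0% | 10.2-10.9% | 10.4-11.8% | 10.8-13.4% |
| 20% | 20.0% | 20.4-21.7% | 20.8-23.2% | 21.4-25.6% |
| 30% | 30.0% | 30.6-32.3% | 31.0-34.1% | 31.6-36.7% |

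The largest gap is 36.7 − 30 = 6.7 points. Up to *k* = 3 the largest is 34.1 − 30 = 4.1 points. At *k* = 1, *S* reduces to exp(−*hT*) and there is no bias. A ratio below 1 would reverse the sign.

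For scale, the 95% half-width of a 20% proportion is 1.96 × √(0.2 × 0.8/250) = 5.0 points if all 250 patients were prospective. It is 7.0 points with 125. The protocol does not give the prospective share.

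**The case against.** The strongest reply is that the rule may be harmless. The sentence just before it can be read as keeping chart collection going unless there is a refusal. The text limits data to those already collected only for withdrawal of consent. Nothing in section 4.4 or 4.5 says that patients are censored at a missed visit, and the rule speaks of visits in the plural, so one absence need not be enough. Section 5.1 already collects current status and last contact date, which would support sound censoring.

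Much of this stands: informative censoring is a risk here, not something the plan demonstrably does. It does not remove the point. The conclusion drawn from that preceding sentence is that non-attenders are lost, and no text tells sites to keep completing status, restart and progression afterwards.

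Three stronger readings are tempting and are not supported.

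- A reader might infer a flat contradiction, that the study has no visits to miss. Only study-specific visits are excluded; the defect is an undefined term.
- A reader might infer that missed follow-up is itself a named outcome, or that COVID-19 mortality will be understated. Section 3.2 names delays and modifications, and its mortality measure is status at discharge, which a later missed appointment does not change.
- A reader might set 30-50% mortality in 10-30% of patients against 10% in the rest. That gives 0.1 × 0.3 + 0.9 × 0.1 = 12% up to 0.3 × 0.5 + 0.7 × 0.1 = 22%, where the rule would show 10%. This places every missed visit at time zero and implies hazard ratios of ln 0.7/ln 0.9 = 3.4 to ln 0.5/ln 0.9 = 6.6. No figure in the documents supports those inputs.

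**Conclusion.** The point holds as a defect in the definition of loss to follow-up. Attendance at unspecified visits is the wrong criterion for a study whose only source is the chart, and following the rule literally could discard outcomes that the chart contains. The exposure is confined to one secondary objective in the prospective part.

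The size is unknown. Understatement of 6-month Kaplan-Meier mortality would be 0 to about 7 percentage points over the assumed range, and about 4 or less for hazard ratios up to 3. In the cases worked, the bias for ratios up to 3 is smaller than the sampling error even with 250 patients. These figures assume that sites stop extraction at the missed visit and that later deaths go unseen. They also assume constant hazards and higher risk after non-attendance. The effect on mean delay is likely to be downward but has not been sized. Log-rank comparisons could also be distorted if attendance differs between groups. The change is worth making because it is cheap and the loss is avoidable.

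**What to change.** Replace the sentence on non-attendance in section 4.4 with a rule of this kind:

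- A missed routine visit is recorded as a follow-up delay, not as loss.
- Vital status, treatment restart and progression continue to be taken from the medical record up to 6 months from inclusion.
- A patient is lost to follow-up only when the record has no later entry or contact. For overall survival, that patient is censored at the last date known alive.
- The number of patients lost is reported.

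Keep the consent-withdrawal rule as written. Time to progression needs its own stated censoring date, which this wording does not settle.

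The variables needed are already listed in section 5.1, so there is no new procedure or data source. The cost is one replaced sentence and slightly more chart extraction for patients who miss appointments.
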